SA 3: Compare the ankle OA clinical and biomechanical outcome measures for the control shoe, RB shoe, and AFO to a healthy control group wearing control shoes. This will determine the difference in clinical and biomechanical outcomes related to the presence of OA.

Methods: We will enroll 100 participants with ankle OA and 50 control participants without lower limb pain. Three study groups will participate in this project. Study group 1 is a single day study and have images taken using our biplane fluoroscopy system. Study group 2 is a three month take home, and Study group 3 is a three month take home and will have images taken using our biplane fluoroscopy system. At visit-1 all participants will do baseline measures (questionnaires and functional assessments, including **SSWS**) and have a CT scan. During the initial visit, group 1 will participate in a biplane assessment. Participants in Study group 2 & 3 will be assigned to a randomly selected order of footwear (RB shoe, control shoe or an AFO). Each footwear condition will be worn for a three-week trial period at-home/in-community (one-week acclimation, two-weeks continuous wear). Participants will complete brief weekly pain assessments and wear a step counter. At visit-2 participants will do a pain rating, repeat the questionnaires and SSWS test, and group 3 will have images taken using our biplane fluoroscopy system. Participants will continue wearing the step-counter during a one week washout period. For the next three weeks, participants will repeat the at-

home/in-community procedures (step counter, weekly pain rating) and come to the VA to repeat the visit-2 procedures. The same process will be repeated for the third footwear condition.

List of Abbreviations

Provide a list of all abbreviations used in the protocol and their associated meanings.

AE - adverse event

AFO - ankle-foot orthosis

CT - computed tomography

mSv - millisievert

OA - osteoarthritis

RB - rocker bottom

ROM - range of motion

ROP - report of other problem

SAE - serious adverse event

SSWS - self-selected walking speed

UW/HMC - University of Washington/Harborview Medical Center

Contents

Protocol Title: Do Rocker Bottom Shoes and Ankle-Foot Orthoses Reduce Pain and Improve Mobility for Ankle Osteoarthritis Patients?..... 6

1.0 Key Study Personnel..... 6

2.0 Introduction..... 6

3.0 Specific Aims and Hypotheses..... 7

4.0 Resources and Personnel..... 8

5.0 Study Procedures..... 8

 5.1 Study Design..... 8

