5.4 Inclusion/Exclusion Criteria

Our targeted range for the total number of study completions is up to 150.

Inclusion Criteria:

Participants with ankle OA:

1. radiographic evidence of tibiotalar OA
2. age 18 years or older
3. able to stand and walk for about an hour (with breaks) and at least 15m (about 50ft) at a time without difficulty
4. minimum pain 3+/ 10

Control participants without OA:

1. age 18 years or older
2. able to stand and walk for about an hour (with breaks) and at least 15m (about 50ft) at a time without difficulty

Exclusion Criteria: all participants

1. subtalar joint arthritis
2. prior ankle joint replacement or fusion on the foot of interest, or recent (<1 year) surgical, neurological, rheumatologic, or lower limb musculoskeletal problem (e.g., current foot ulcer, severe hip/knee OA, terminal illness, etc.) that impairs an individual's ability to do the walking tests
3. current user of AFO or rocker bottom shoe and has either been prescribed by doctor or is not willing to stop using the device for three months
4. plans to undergo surgical treatment for ankle OA within three months
5. inability to walk unassisted during short, repeated walking trials
6. rheumatoid arthritis
7. inadequate cognitive or language function to consent or to participate
8. no phone number or stable mailing address
9. currently incarcerated
10. currently pregnant
11. open wounds on the foot or ankle
12. below- knee surgery in the past 60 days

Additional Exclusion Criteria, Controls only:

1. Ankle pain or ankle OA in addition to the above exclusionary criteria

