This process establishes a tibial anatomical coordinate system and a talar coordinate system for measuring talocrural joint ROM. These same methods will be used to measure talonavicular, naviculocuneiform, and the first cuneometatarsal kinematics. By performing this template matching algorithmically, we can ensure consistency in post processing of anatomical coordinate systems between subjects.

Statistical Methods:

For **Specific Aim 1**, linear mixed effects regression will be carried out to test for differences in mean step count, self-selected walking speed, physical function or pain (the dependent variables) by intervention, (control shoe vs. RB shoe vs. AFO, the independent fixed effect) with study subject as a random effect. If the omnibus test for the association between outcome variables and intervention is significant, pairwise comparisons will be carried out to assess differences in mean outcomes between the RB shoe or the AFO and the control shoe (Hypothesis 1.1) and between the RB shoe and the AFO (Hypothesis 1.2).

For **Specific Aim 2**, linear mixed effects regression will be used as above to examine differences in mean [sagittal plane] ROM (the dependent variable) by intervention (control shoe, RB shoe, AFO; the independent fixed effect) with subject and subject by intervention interaction as random effects. If the omnibus test for association between [sagittal plane] ROM and foot intervention is significant, pairwise comparisons will be carried out to assess differences in mean [sagittal plane] ROM between the RB shoe, the AFO, and the control shoe (Hypothesis 2.1). Secondary analyses will be carried out using methods similar to those described above to determine if the interventions affect frontal and transverse plane joint ROM.

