For **Specific Aim 3**, hypotheses 3.1 and 3.2, the above model will be modified with the definition of the independent fixed effect, foot intervention, having an additional category representing the healthy control group. Post-hoc comparisons will focus on differences in mean step count, self-selected walking speed, physical function, pain or [sagittal plane] ROM between RB shoe or AFO and the healthy control subjects wearing the control shoes. Additional secondary analysis will be carried out using linear mixed effects regression to determine if pain (the dependent variable) correlates with [sagittal plane] ROM (the independent fixed effect, averaged over trial) and step count (the dependent variable) correlates with pain (the independent fixed effect) with study subject as a random effect in both sets of models. To determine if the mean differences in outcome by intervention (AFO vs. RB shoe) varies by OA severity, the regressions described above will be modified by adding two additional independent co-variates: OA severity and OA severity X intervention. The significance of the latter interaction term suggests that OA severity may influence outcome differences by intervention.

Power Analysis:

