Ten thousand datasets were generated using mean [sagittal] ROM for the control foot of 15.3 degrees, between subject SD of 2.0 degrees, and within subject SD of 2.4 degrees.⁸⁴ Power was estimated for sample sizes of 15 and 20 subjects and for a 1.5 degrees and 2.0 degrees difference in [sagittal] ROM between the control shoe and the RB shoe or AFO. Hypothesis testing for each bootstrapped sample for the reduction in ROM was carried out using a linear mixed effects regression of [sagittal] ROM (the dependent variable) on foot (ROM or AFO vs. control) with study subject and subject by intervention interaction as random effects. Power was estimated by determining the number of tests that were significant at the 0.05 level using the likelihood ratio test. The analysis indicated that if the footwear induces a 1.5 degrees change in ankle [sagittal] ROM then a sample size of 20 or 15 subjects results in 94% or 84% power, respectively. If the change in ROM is 2.0 degrees, then even with only 15 subjects the study has 98% power (Table 2). Note that we expect the change in [sagittal] ROM to be significantly more than 1.5 degrees but even for this small difference our study is adequately powered with 25 subjects. Based on these results, we plan to enroll 30 subjects into the

study and expect several to drop out leaving a sample size of at least 25 subjects and the study power greater than 94% (Table 2).

Simulated [sagittal] ROM difference between the control shoe and RB shoe or AFO	Number of subjects	Estimate power
1.5 degrees	15	84%
2.0 degrees	15	98%
1.5 degrees	20	94%

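### The SA 3 model makes no allowance for a different variance in healthy controls, so its OA-versus-healthy pain intervals are likely to be misstated (too wide at the 100:50 enrolment target)

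*Combined protocol and SAP*

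**What the plan says.** Section 5.6, Statistical Methods, builds SA 3 on the models for SA 1 and SA 2. The SA 1 model takes intervention as "the independent fixed effect) with study subject as a random effect". The SA 2 model for ROM is fitted "with subject and subject by intervention interaction as random effects". SA 3 then modifies the model through "the independent fixed effect, foot intervention, having an additional category representing the healthy control group", and its post-hoc comparisons set RB shoe or AFO against healthy controls on step count, walking speed, function, pain and sagittal ROM. No group-specific variance, robust standard error or variance check is mentioned.

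Section 5.4 requires "minimum pain 3+/ 10" of OA participants and lists for controls the exclusion "Ankle pain or ankle OA in addition to the above exclusionary criteria". Both groups share the same age and walking criteria.

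On size, the Abstract says: "We will enroll 100 participants with ankle OA and 50 control participants without lower limb pain". The table in section 5.1 agrees. The power analysis in section 5.6 instead plans 30 enrolled with at least 25 remaining, and gives no control number. Its ROM inputs are a "between subject SD of 2.0 degrees, and within subject SD of 2.4 degrees", with no separate values for OA and healthy.

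**The concern.** A linear mixed model with only these terms estimates one set of variance components and applies it to everyone. That is harmless if the groups have similar spread, or nearly so if the weights happen to balance. It fails when spread and group size both differ. The larger group then dominates the pooled variance, and the standard error of the between-group contrast is wrong in a direction set by which group is larger and which is more variable.

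Pain is where the documents give a reason to expect this. The rating runs from 0 to 10 (section 5.5, Brief Pain Rating). Controls are screened to sit near its floor, where there is little room to vary. Hypothesis 3.1 compares the numeric pain rating and PROMIS pain interference with controls, so stated hypotheses are affected. SA 3 is meant to determine the size of the OA-related difference, so interval width matters even where significance is not in doubt.

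**Working it through.** **The plan's own figure.** The only design calculation is for the within-OA ROM contrast. With k trials per footwear, power = Φ(δ / [2.4·√(2/(n·k))] − 1.96). The plan does not give k. With k = 3 and no interaction variance (both assumed), the results are 84.2% (n = 15, 1.5°), 97.7% (n = 15, 2.0°) and 92.8% (n = 20, 1.5°), against the stated 84%, 98% and 94%. With k = 1 they are 40%, 63% and 51%. This figure says nothing about SA 3, which has no design calculation.

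**Inputs for SA 3.**
- From the documents: 100 OA and 50 controls (Abstract, section 5.1); 25 or 30 OA (section 5.6, power analysis).
- ICC = 2.0² / (2.0² + 2.4²) = 4 / 9.76 = 0.41. This comes from ROM and is borrowed for the other outcomes; 0.7 is tried as well.
- Assumed: three values per OA participant (one per footwear), one per control, a random-intercept model, and the healthy/OA SD ratio r.

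**Formulas.** Set the OA total variance to 1, so the true components in OA are s₀ = 0.59 (residual) and t₀ = 0.41 (subject). The true variance in controls is r². The common-variance REML fit settles at the s and t that minimise

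(n₁−1)·[2 ln s + 2s₀/s + ln(s+3t) + (s₀+3t₀)/(s+3t)] + (n₂−1)·[ln(s+t) + r²/(s+t)].

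Model SE = √[(s+t)(1/n₁ + 1/n₂)]. True SE = √(1/n₁ + r²/n₂). The actual level of a nominal 5% test is 2Φ(−1.96 × model SE / true SE).

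**Example.** At 100:50 with r = 0.5, the fit gives s + t = 0.870. Model SE = √(0.870 × 0.03) = 0.1615. True SE = √(0.01 + 0.25/50) = √0.015 = 0.1225. The ratio is 1.32.

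| OA:healthy | r | Model SE | True SE | Ratio | Actual level |
|---|---|---|---|---|---|
| 100:50 | 0.25 | 0.159 | 0.106 | 1.50 | 0.3% |
| 100:50 | 0.5 | 0.162 | 0.122 | 1.32 | 1.0% |
| 100:50 | 0.67 | 0.165 | 0.138 | 1.20 | 1.9% |
| 100:50 | 1 | 0.173 | 0.173 | 1.00 | 5.0% |
| 100:50 | 1.25 | 0.182 | 0.203 | 0.90 | 7.9% |
| 100:50 | 1.5 | 0.193 | 0.235 | 0.82 | 10.6% |
| 30:50 | 0.25 | 0.183 | 0.186 | 0.98 | 5.4% |
| 30:50 | 0.67 | 0.203 | 0.206 | 0.99 | 5.3% |
| 25:50 | 0.25 | 0.187 | 0.203 | 0.92 | 7.1% |
| 25:50 | 0.5 | 0.200 | 0.212 | 0.94 | 6.5% |
| 25:50 | 0.67 | 0.212 | 0.221 | 0.96 | 6.0% |

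With ICC 0.7 and r = 0.5, the ratios are 1.28 (100:50), 0.94 (30:50) and 0.90 (25:50).

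**Simulation check.** 250 fitted datasets per setting at 100:50, ICC 0.41. For r = 0.25 the mean model SE was 0.158 against an empirical SD of 0.100, with 0.4% rejections. For r = 1 both were 0.174, with 5.6% rejections.

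**What it does to an interval.** At 100:50 with r = 0.5, the 95% half-width is 1.96 × 0.1615 = 0.317 OA SDs where 1.96 × 0.1225 = 0.240 is correct.

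**The case against.** The strongest reply is that the documents never state a common variance; they are silent. That is true, and the point rests on the default meaning of the terms listed. Since nothing in section 5.6 departs from that default, it remains the natural reading.

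A reader might infer that every OA-versus-healthy standard error in SA 3 is wrong. The documents do not support this. Section 5.4 separates the groups on pain only. Their walking and age criteria are the same, and no SD by group is given for step count, speed, function or ROM. Even for pain, the floor of 3 of 10 also trims the OA distribution at entry, so the SD ratio is not known.

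A reader might also infer an inflated false-positive rate. For pain at 100:50 the error runs the other way, and screening has already separated the groups, so a wider standard error is unlikely to change the verdict. With less variable controls, inflation needs OA numbers well below control numbers. At 30:50 it is slight at ICC 0.41 (6.6% at ICC 0.7 with r = 0.5). At 25:25, simulation gave standard errors 4% to 16% too large for SD ratios from 0.8 down to 0.25. The 25:50 case pairs a post-dropout OA figure with the full control group, a pairing the plan does not state.

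Nor is 100 OA with three values each secure. Section 5.5 does not confine the single-day group to controls, so 100 is an upper bound. The calculation also uses a random intercept only, whereas the ROM model adds a subject-by-intervention term. All of this limits the claim's reach and precision. It does not remove the problem for pain.

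**Conclusion.** The point holds for the pain contrasts and is minor. The SA 3 model as written pools variance across groups that eligibility places at opposite ends of the pain scale. At 100:50 the OA-versus-healthy pain standard errors would be about 20% to 50% too large for SD ratios of 0.67 to 0.25. The consequence is a misstated interval for the OA-related difference; a changed test result is unlikely.

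For the other outcomes it is an open question. If controls were less variable, the error at ICC 0.41 would be conservative at 100:50, close to nil at 30:50, and about 4% to 8% too small at 25:50. If controls were more variable at 100:50, with SD ratios of 1.25 to 1.5, a nominal 5% test would run at about 8% to 11%. Because SA 3 does not fix its group sizes, neither direction nor size can be settled from the documents.

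These figures rest on assumed SD ratios, an ICC taken from ROM, and three values per OA participant against one per control.

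**What to change.** In the SA 3 paragraph of section 5.6, keep the four-level model and add that variance is estimated separately for OA and healthy participants, with small-sample degrees of freedom (Satterthwaite or Kenward-Roger) for the contrasts.

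- Where a control gives one value, only a total variance can be estimated for that group, so one extra parameter suffices.
- Where controls give repeated ROM trials in one footwear, let the between-subject and the trial-level variance each differ by group. Subject and subject-by-intervention variance cannot be separated in controls.
- If control pain variance is near zero and the model does not fit, use cluster-robust standard errors by subject, and name this fallback in advance.
- State the number of OA and control participants expected in each SA 3 comparison, and reconcile 100:50 with the 30 enrolled in the power analysis.

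The cost is one or a few variance parameters and a slight loss of precision if the variances are in fact equal. Under the assumptions above, the SE at 100:50 with r = 0.5 falls from 0.162 to 0.122, and at r = 1 it stays at 0.173. No data, visit or hypothesis changes.

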3.0 Specific Aims and Hypotheses

The purpose of this study is to evaluate the ability of RB shoes and AFOs to improve mobility, by alleviating pain and reducing joint motion when compared to a standard shoe. This study has three specific aims (SA):

SA 1: Compare the daily step count, **self-selected walking speed (SSWS)**, and self-reported outcomes from a set of questionnaires assessing pain and mobility before and after wearing a control shoe, RB shoe and a AFO. Each footwear condition will be worn over a three-week period (one-week acclimation, two-week trial period). This will indicate how subjects respond to these treatment conditions – what their pain levels are compared to baseline, how they self-report functional change, and from their step count, a quantitative measure of their mobility in the treatment footwear.

Hypothesis 1.1: For ankle OA subjects, the RB shoe and AFO will exhibit increased step count, self-selected walking speed, improve physical function, and reduced pain when compared to a control shoe.

Hypothesis 1.2: For ankle OA subjects, the AFO will increase step count, self-selected walking speed, improve physical function, and reduce pain more than the RB shoe or control shoe.

SA 2: Evaluate the effect of a control shoe, a RB shoe and a AFO on the front-to-back ROM of the foot and ankle. This will determine how these devices shield the ankle from motion – potentially protecting it, and if they impose abnormal motion on adjacent foot joints – potentially exposing them to additional wear and increasing their risk for long term OA development.

Hypothesis 2.1: For ankle OA subjects, the sagittal ROM of the talocalcaneal, talocrural, talonavicular, naviculocuneiform, and first cuneometatarsal joints will be less when wearing the AFO than the RB shoe, which will be less than OA subjects wearing the control shoe.

SA 3: Compare the ankle OA clinical and biomechanical outcome measures for the control shoe, RB shoe, and AFO to a healthy control group wearing control shoes. This will determine the difference in clinical and biomechanical outcomes related to the presence of OA.

Hypothesis 3.1: For ankle OA subjects, daily step count, self-selected walking speed, PROMIS physical function, and FAOS will be less, while the PROMIS pain interference, AOS-FAM, and numeric pain rating will be greater than the control subjects wearing the control shoes.

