Hypothesis 3.2: For ankle OA subjects, the sagittal ROM of the talocalcaneal, talocrural, talonavicular, naviculocuneiform, and first cuneometatarsal joints when wearing RB shoes or AFOs will be less than the [sagittal] ROM of the control subjects wearing the control shoes.

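### Aim 3 names only device-versus-healthy contrasts; for the Hypothesis 3.1 outcomes these add a footwear effect to the OA difference, and the same-shoe contrast is not named

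*Combined protocol and SAP*

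**What the plan says.** Specific Aim 3 (Abstract and section 3.0) compares "outcome measures for the control shoe, RB shoe, and AFO to a healthy control group wearing control shoes". Its purpose is given as: "This will determine the difference in clinical and biomechanical outcomes related to the presence of OA".

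Hypothesis 3.1 concerns clinical outcomes: "For ankle OA subjects, daily step count, self-selected walking speed, PROMIS physical function, and FAOS will be less", while pain interference, AOS-FAM and "numeric pain rating will be greater than the control subjects wearing the control shoes". It fixes the healthy group's footwear and gives none for the OA subjects.

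Hypothesis 3.2 concerns sagittal range of motion (ROM) and does fix the OA footwear: ROM of the listed "joints when wearing RB shoes or AFOs will be less than the [sagittal] ROM of the control subjects wearing the control shoes".

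Section 5.6 (Statistical Methods, Specific Aim 3) handles both hypotheses by adding a healthy-control category to the footwear factor. That gives four levels: OA in control shoe, OA in rocker bottom (RB) shoe, OA in AFO, and healthy. The post-hoc focus is then one comparison for step count, walking speed, physical function, pain or "ROM between RB shoe or AFO and the healthy control subjects wearing the control shoes". OA in the control shoe is not among the comparisons named for this aim.

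**The concern.** The aim lists three OA footwear conditions and asks what difference goes with having OA. The analysis text names two of those conditions, and they are the two in which footwear also differs between the groups. The condition that holds footwear constant is left out.

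For Hypothesis 3.2 this does no harm, because that hypothesis is about OA subjects in a device. For Hypothesis 3.1 the named contrast answers a different, legitimate question: how much deficit remains once an OA subject wears the device. The plan also expects the devices to help, since Hypothesis 1.1 says "the RB shoe and AFO will exhibit increased step count" and predicts gains in walking speed, function and pain. The better the devices work under Aim 1, the smaller the difference seen under Hypothesis 3.1.

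**Working it through.** The plan gives no power or sample size for Aim 3, so there is no figure to reproduce. The check is contrast algebra, followed by an illustration.

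**1. Decomposition.** Write m(group, footwear) for a mean. Then

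m(OA, device) − m(healthy, control shoe) = [m(OA, control shoe) − m(healthy, control shoe)] + [m(OA, device) − m(OA, control shoe)].

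The left side is the contrast named in section 5.6. The first bracket is the same-shoe OA difference. The second is the within-OA footwear effect, which for the clinical outcomes is the Aim 1 pairwise comparison.

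**2. Signs.** Hypothesis 3.1 expects the first bracket to be unfavourable. Hypothesis 1.1 expects the second to be favourable. With deficit D and footwear benefit F, the named contrast has size D − F and the same-shoe contrast has size D. If a device worsens an outcome, F is negative and the deficit is overstated instead.

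**3. Estimability.** OA in control shoe is already a level of the planned model, so the same-shoe contrast needs no new term. Both contrasts need healthy subjects to provide the outcome in the control shoe.

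**4. Illustration.** Inputs:
- From the documents: 100 OA and 50 control participants (section 5.1, an enrolment ceiling); at least 25 completers (section 5.6, Power Analysis, written for ROM).
- Assumed: D = 0.5 SD; F = 0.1, 0.2 or 0.3 SD; equal SDs; one mean per subject per condition; two-sided 0.05.

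Power comes from the noncentral t distribution with noncentrality (effect in SD) / √(1/n₁ + 1/n₀).
- 100 versus 50: √(0.01 + 0.02) = 0.1732, 148 degrees of freedom.
- 25 versus 50: √(0.04 + 0.02) = 0.2449, 73 degrees of freedom.

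| Contrast | Effect (SD) | Noncentrality, 100 vs 50 | Power | Noncentrality, 25 vs 50 | Power |
|---|---|---|---|---|---|
| Same-shoe | 0.5 | 2.887 | 82% | 2.041 | 52% |
| Named, F = 0.1 | 0.4 | 2.309 | 63% | 1.633 | 36% |
| Named, F = 0.2 | 0.3 | 1.732 | 41% | 1.225 | 23% |
| Named, F = 0.3 | 0.2 | 1.155 | 21% | 0.816 | 13% |

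With a larger assumed deficit of 0.8 SD at 100 versus 50, the same-shoe contrast has over 99% and the named contrast 98%, 93% and 82%, so the loss is much smaller. The illustration is not meant for the pain rating. Section 5.4 requires pain of at least 3 out of 10 in OA subjects and excludes controls with ankle pain, so that difference is largely built in by eligibility.

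**5. ROM.** The Power Analysis considers a footwear effect of 1.5 or 2.0 degrees. An effect of that size would move the named ROM contrast by the same amount with no OA difference at all. That is part of what Hypothesis 3.2 asks, so it is not an error there. It does mean that the named contrast alone does not give the OA difference in biomechanical outcomes, which Specific Aim 3 also covers.

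**The case against.** The strongest reply is that a contrast has gone unnamed and no analysis is wrong. Much of this stands.

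- **Nothing is forbidden.** The text says where the comparisons will focus. It does not rule out others, the aim itself lists the control shoe, and the model contains it. A reader might infer that the plan excludes the same-shoe comparison; the documents do not say so.
- **No false OA effect.** A reader might infer that the named contrast could manufacture an OA deficit. In the direction Hypothesis 1.1 predicts, it shrinks the deficit, so it is a conservative test of Hypothesis 3.1. Because that hypothesis leaves OA footwear open, the device contrasts are also admissible as additional tests.
- **The OA difference is recoverable.** Subtracting the within-OA contrast gives the same point estimate if subjects and model are the same. That contrast comes from Aim 1 for the clinical outcomes, and for ROM from Aim 2, which examines "differences in mean [sagittal plane] ROM between the RB shoe, the AFO, and the control shoe". A standard error is obtainable too. Section 5.6 plans means and SDs for each intervention, and OA and healthy subjects are independent groups, so a two-sample standard error follows once the healthy group's mean, SD and number are reported. It would be too strong to say that no test is possible without the direct contrast.
- **The same-shoe contrast is not a pure OA effect either.** Under section 5.5, take-home OA participants are assessed after three weeks in the shoe, while study group 1 attends for one day. If healthy subjects are measured at a single visit, which the documents do not settle, OA is mixed with wear time.
- **Healthy-group data are unclear.** Study group 1's activity list omits the questionnaires, although the Abstract gives baseline questionnaires to everyone. Walking speed may be taken in the participant's own footwear. Take-home step counting is described for OA participants, yet group 1 is said to return a StepWatch. This limits both contrasts equally.

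What remains is that the plan does not say which comparison tests Hypothesis 3.1, and the comparisons it does name are not the ones that match the aim's purpose.

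**Conclusion.** The point holds as a gap in the analysis text. The named post-hoc contrast suits Hypothesis 3.2. For the Hypothesis 3.1 clinical outcomes it is the same-shoe OA difference plus a footwear effect, and it understates the OA-related difference by the amount of any device benefit. That follows from algebra and needs no assumption beyond the direction given in Hypothesis 1.1.

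The size is not known from the documents. The power figures rest wholly on assumed effects, and 100 versus 50 is a ceiling. At 25 versus 50 even the same-shoe contrast reaches only about 52% for a 0.5 SD deficit. No inflated error rate is claimed. Correcting this is worthwhile because a stated aim lacks its direct comparison and supplying it costs almost nothing.

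**What to change.** In section 5.6, Specific Aim 3:

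1. State that Hypothesis 3.1 is tested first by OA in control shoe versus healthy in control shoe, for each outcome that healthy subjects provide in the control shoe, and list those outcomes. For any other outcome, say that neither this contrast nor the device contrasts can be run.
2. Report the same contrast for ROM.
3. Keep RB shoe and AFO versus healthy as the test of Hypothesis 3.2, and as a secondary comparison for Hypothesis 3.1, labelled as the deficit remaining in the device.
4. State when each group is measured in the control shoe, and note in the interpretation that the same-shoe contrast mixes OA with wear time if healthy subjects are seen once and OA subjects after three weeks.

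The cost is wording and one more comparison per outcome from a level already in the model. No new visits or data are needed for the listed outcomes.

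### The OA-severity analysis asks about AFO versus RB shoe but, as written, tests an interaction term that also contains the control shoe

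*Combined protocol and SAP*

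**What the plan says.** All of this is in section 5.6, under Statistical Methods.

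- **The question.** The severity analysis, at the end of the Specific Aim 3 paragraph, is introduced as "To determine if the mean differences in outcome by intervention (AFO vs. RB shoe) varies by OA severity".
- **The model.** "the regressions described above will be modified by adding two additional independent co-variates: OA severity and OA severity X intervention". This is the only modification given.
- **The regressions being modified.** For Aim 1, intervention is "control shoe vs. RB shoe vs. AFO, the independent fixed effect) with study subject as a random effect". For Aim 2, outcomes are compared "by intervention (control shoe, RB shoe, AFO; the independent fixed effect) with subject and subject by intervention interaction as random effects". For Aim 3, the same factor is redefined as "having an additional category representing the healthy control group".
- **How the result is read.** "The significance of the latter interaction term suggests that OA severity may influence outcome differences by intervention".
- **Follow-up contrasts.** For the main effect of intervention in Aim 1, the plan says "If the omnibus test for the association between outcome variables and intervention is significant, pairwise comparisons will be carried out", and these include RB shoe against AFO. No such step is given for the severity interaction.

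The documents do not say how OA severity is graded or coded, and they give no sample size, power or error rate for this analysis.

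**The concern.** With severity entered linearly, the stated question is one contrast: the severity slope under AFO minus the severity slope under RB. The stated test is the interaction term as a whole. With three intervention levels, that term tests whether the severity slopes under control shoe, RB and AFO are all equal. It can be significant because the control-shoe slope differs from the other two, while the AFO and RB slopes are identical.

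That pattern is not far-fetched here. The introduction proposes that both devices work by limiting joint motion, so severity could plausibly alter the benefit of both in a similar way. A reader who takes a significant term as the answer to the question just posed could then conclude that severity bears on the choice between AFO and RB when it does not. Conversely, if severity matters only for AFO against RB, the wider test has less power than the contrast.

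The four-level Aim 3 model adds a gap. OA severity is not defined for people without OA, so the healthy-control part of the interaction cannot be estimated. This does not harm the AFO–RB contrast, which lies within OA participants, but the plan should say who enters the model.

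**Working it through.** The plan states no figure for this analysis, so there is none to reproduce. The check has three parts.

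**1. Degrees of freedom.** Linear severity crossed with three intervention levels gives 3 − 1 = 2 df. Adding healthy controls gives a nominal third df, but it is not estimable, so 2 remain. The AFO–RB contrast has 1 df.

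**2. General size (large-sample chi-square, two-sided 5%).** Take a severity effect that a correctly aimed 1-df test detects with 80% power.

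- Noncentrality = (1.96 + 0.842)² = 7.85.
- Rejection probability at 7.85: 80% with 1 df, 70.9% with 2 df.

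This has two readings:

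- *The effect is common to both devices and AFO minus RB is constant.* The 2-df term is significant about 71% of the time. The AFO–RB contrast is null and rejects 5%.
- *The effect lies wholly in AFO minus RB.* Power falls from 80% on the contrast to about 71% on the 2-df term.

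**3. On the scale of the plan's ROM figures.** The Power Analysis gives "control foot of 15.3 degrees, between subject SD of 2.0 degrees, and within subject SD of 2.4 degrees". It does not give the number of trials per condition, k, so k was back-solved from the plan's Aim 2 powers, using SE = 2.4 × √(2/(n·k)):

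| k | n=15, 1.5° (plan 84%) | n=15, 2.0° (plan 98%) | n=20, 1.5° (plan 94%) |
|---|---|---|---|
| 1 | 40% | 63% | 51% |
| 2 | 68% | 90% | 80% |
| 3 | 84.2% | 97.7% | 92.8% |
| 4 | 93% | 99.5% | 98% |

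Only k = 3 comes within 2 points of all three. It is an inference, not a documented value.

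Now assume severity standardised to SD 1, complete data, no extra subject-by-intervention variance, and severity slopes (control, RB, AFO) = (0, b, b), so that AFO minus RB does not depend on severity. The 2-df test is an F test on 2 and 2(N − 2) df with noncentrality

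λ = (N − 1) × (2/3) × b² / (2.4²/k).

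Example: N = 25, b = 0.5, k = 3 gives λ = 24 × 0.667 × 0.25 / 1.92 = 2.08, and a rejection rate of 22%.

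| N (source) | b = 0.5° per SD, k = 3 | b = 1.0° per SD, k = 3 |
|---|---|---|
| 25 (Power Analysis, after dropout) | 22% | 71% |
| 30 (Power Analysis, enrolled) | 26% | 80% |
| 100 (section 5.1, OA target) | 74% | >99% |

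Over the undocumented k, at b = 0.5: N = 25 runs from 10% (k = 1) to 81% (k = 15), and N = 100 from 30% to above 99%.

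Simulation (20,000 runs per scenario, k = 3) put the 1-df AFO–RB contrast at 4.8% to 5.3% in every common-effect scenario, and a model restricted to AFO and RB at 4.7% to 5.3%. With b = 0 both tests sit at about 5%. With slopes (0, −0.5, +0.5), where the devices truly differ, the contrast has more power than the 2-df term: 67% against 56% at N = 25, and 75% against 65% at N = 30.

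**The case against.** The strongest reply is that the plan already means a two-level factor. Elsewhere in the same section, the parenthesis after the word intervention lists the levels of the factor; here it lists only AFO and RB shoe. Two added covariates, one of them the interaction, would fit one severity column and one interaction column. On that reading the term has 1 df, is exactly the contrast wanted, and the problem disappears. This is a fair reading and cannot be excluded. It is not what the model sentence says, however: that sentence reuses the earlier regressions and states no restriction. Two competent analysts could follow the text and test different hypotheses.

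Second, the plan's closing sentence is hedged and names no device pair, and it is literally true of a 2-df test. That stands. A reader might infer that the plan would declare severity decisive for choosing between AFO and RB; the text does not go that far. The mismatch is between the question posed and the test named to answer it.

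Third, a global test followed by contrasts would be in keeping with the Aim 1 convention. It would, but no contrast step is stated for this interaction.

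Fourth, the sizes are hypothetical. That also stands: the documents give no severity effect or scale, and the general 71% would apply to any 2-df test set against a 1-df question.

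Finally, the analysis is secondary and no hypothesis in section 3.0 mentions severity. That limits the importance of the point but does not remove it.

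**Conclusion.** The point holds as a mismatch between question and test, conditional on the plain reading that intervention keeps its earlier levels. On that reading, any severity effect shared by both devices raises the chance of a significant term above 5% while AFO minus RB is constant. The direction does not depend on the assumed numbers; the size does. The illustrative figures are about 71% against 5% for a common effect with 80% power at 1 df, and a power loss from 80% to 71% when only AFO minus RB varies. On the ROM scale, with k = 3 and b = 0.5, the rate is 22% at 25 subjects and 74% at 100. All assume linear severity and slopes that the documents do not supply.

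Two stronger readings are not supported. A reader might infer that the term will be significant whenever severity alters a device's effect against the control shoe; the 10% and 22% figures show otherwise. A reader might also cite a further power loss from a 3-df test in the four-level model; the third df is not estimable, so no such test exists.

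No primary comparison is affected. This is a clarification worth making before analysis.

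**What to change.** Amend the severity paragraph in section 5.6 to state that:

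1. The severity model is fitted in OA participants only, since severity is not defined for healthy controls.
2. The test is the single contrast of the severity slope under AFO minus the severity slope under RB, reported as an estimate with a confidence interval.
3. Device-versus-control-shoe differences by severity are reported as separate contrasts and are not used to answer the AFO–RB question.
4. How severity is graded and coded. If it is categorical, the AFO–RB-by-severity test has more than 1 df and should be written out accordingly.

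If a two-level model was always intended, one clause saying that this analysis uses only the AFO and RB conditions would resolve the main point; in the simulations that model also held its error rate near 5%. The cost is wording only: no new data, visits or participants.
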